A		[STUDY IVR USE PERIOD]		TERMINATION
B		[NO IVR (SAME STUDY VISITS AS GROUP A)]				

Study Objectives

Primary Objectives

- Evaluate the safety of the study IVR in HIV-uninfected women over 12 weeks of use
- Evaluate the adherence to the study IVR in HIV-uninfected women over 12 weeks of use

Primary Endpoints:

- Evidence of Grade 2 or higher genitourinary events as defined by the Division of AIDS (DAIDS) Table for Grading the Severity of Adult and Pediatric Adverse Events, Version 1.0, Dec 2004 (Clarification dated August 2009), Addendum 1 (Female Genital Grading Table for Use in Microbicide Studies)
- For women randomized to the study IVR arm, participant report of frequency of study IVR removal (voluntary and involuntary) and duration without IVR inserted in vagina over 12 weeks of use

Secondary Objectives

- Describe changes in sexual behavior and changes in vaginal hygiene practices in the study IVR vs. no IVR group over 12 weeks of use/non-use
- Evaluate the acceptability of the study IVR in HIV-uninfected women over 12 weeks of use
- Measure vaginal flora characteristics, and descriptively examine changes in these characteristics over the course of study IVR use

Secondary Endpoints

- Per participant report, changes in sexual behavior and vaginal hygiene practices
- For women randomized to the study IVR arm, participant report of acceptability including genitourinary discomfort, ring insertion/removal issues, expulsions (including context of expulsion), and changes in participant and/or partner sexual feeling
- Changes in vaginal flora from enrollment to week 12 as measured by Gram stain Nugent score and quantitative culture (note that these quantitative vaginal cultures will only be available from the US sites, therefore reducing the available sample size for this objective)

Exploratory Objective

- Test candidate biomarkers in the cervicovaginal environment before and after the use of study IVR
- Evaluate the study IVR after 12 weeks of use for the presence of biofilms (US sites only)

Exploratory Endpoint

- Changes in vaginal biomarkers (US sites only)
- Presence of biofilms on study IVR surface (US sites only)

KEY ROLES

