Limited studies have also been conducted to determine the effect of IVR use on vaginal microflora and pathogenic organisms. A study evaluating changes in the quantities of vaginal cells, aerobic and anaerobic bacteria, *Chlamydia trachomatis*, *Gardnerella vaginalis*, yeast, and *Trichomonas vaginalis* was conducted in 59 women using a combined contraceptive vaginal ring made of Silastic[®] with an ethylene vinyl acetate (EVA) core for either a 21, 28, 42, or 56 day cycle.¹⁸ No increases in pathogenic bacteria were found upon examination of vaginal cultures. Another study conducted with a Silastic[®] ring with a polyethylene vinyl acetate core and containing a combined hormonal contraceptive, evaluated the effect of the ring on bacterial flora over 20 cycles of use among 76 women.¹⁹ The investigators found no significant changes in bacterial flora over the course of the study. Two studies conducted among 92 women with NuvaRing[®] showed no adverse effects on vaginal flora as measured by Nugent score.^{20, 21} Interestingly, a NuvaRing[®] study conducted by Veres et al.²⁰ found an increase in hydrogen peroxide (H₂O₂) producing *Lactobacillus* colonies as measured by quantitative culture. Presence of H₂O₂-producing lactobacilli is beneficial to vaginal health and it has been suggested that further studies be conducted to confirm these findings.

The success of IVRs in delivering effective contraceptive and hormone-replacement methods has spurred an interest in developing IVRs expressly for the prevention of HIV. Phase 1/2 safety studies have been conducted by the International Partnership for Microbicides (IPM) for an IVR containing dapivirine, a non-nucleoside reverse transcriptase inhibitor (NNRTI).²²⁻²⁵ The IVRs used in these studies (both active and placebo) have been well tolerated by most study participants.

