MTN-005 will also examine the impact of study IVR use on vaginal flora. Studies have shown that the presence of H₂O₂ producing lactobacilli in the vagina offer a protective effect against sexually transmitted infections.⁵⁵⁻⁶⁰ For example, a study conducted in female sexual contacts of infected men, demonstrated correlation between reduced prevalence of *Chlamydia trachomatis*, *Trichomonas vaginalis*, and symptomatic *Candida* and presence of H₂O₂ producing lactobacilli.⁶¹ Another study highlighted a lower prevalence of *Neisseria gonorrhoeae*, *Chlamydia trachomatis*, and *Trichomonas vaginalis* in women with lactobacilli compared to women with little to no lactobacilli present in the vagina.⁶² Furthermore, longitudinal studies conducted in Kenya⁶⁰ and Malawi⁵⁶, have clearly demonstrated a link between HIV acquisition and changes in vaginal flora. A third study conducted in South Africa showed a correlation between elevated vaginal pH levels and an increased risk of HIV acquisition.⁵⁷ These studies demonstrate a link between vaginal flora and susceptibility to sexually transmitted infections. There are currently no published data on the impact of three-month use of this type of IVR on quantitative measures of vaginal flora. MTN-005 also seeks to assess whether or not the study IVR can harbor organisms that are associated with biofilm formation. Studies have shown that the presence of biofilms can result in the expression of drug resistant genes as well as acute disseminated infection.^{63, 64} Study site staff will perform a biofilm assessment via culture and/or other techniques, depending on site capacity, of the study IVRs when they are collected at the 12-Week Visit or when the IVRs are returned to the study site. The specimens will then be shipped to the Network Laboratory as appropriate. Given the time sensitive nature of specimen handling, the biofilm assessments will only be done at the US sites.

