10.4.4 Changes in Vaginal Flora and Biomarkers

Changes in Nugent scores will be assessed by comparing the Nugent score at enrollment with the one observed at 12 weeks. An abnormal Nugent score is defined as a Nugent score higher than 3 while a normal Nugent score is defined as a score of 3 or less. The proportion of changes between enrollment and week 12 from normal to abnormal will be compared as well as the one from abnormal to normal.

Changes in Nugent score over time are naturally occurring. Based on a sample of 1016 women,⁶⁶ 28.4% of women with a normal Nugent score at enrollment had an abnormal Nugent score 4 months later while 32.8% of women with an abnormal Nugent score at enrollment had a normal Nugent score 4 months later. Therefore, for the purpose of power calculations, we are estimating the proportion of changes in Nugent scores from enrollment to week 12 at 30% in the no IVR arm and this for both from normal to abnormal and from abnormal to normal. Furthermore, we are estimating that 55% and 45% of women will be normal and abnormal, respectively, at enrollment.

The proportion of women with a change in Nugent score from normal to abnormal, at enrollment and 12 weeks, respectively, will be compared between the study IVR and no IVR arms. Assuming that the true proportion of changes in the no IVR arm is 30%, a sample size of 252 women (138 normal women at enrollment and available for the analysis) with a 2:1 randomization will allow detection of an absolute difference of 25% with 80% power (i.e. 30% of women in the no IVR arm and 55% of women in the study IVR arm).

Similarly, the proportion of women with a change in Nugent score from abnormal to normal, at enrollment and 12 weeks, respectively, will be compared between the study IVR and no IVR arms. Assuming that the true proportion of changes in the no IVR arm is 30%, a sample size of 252 women (114 abnormal women at enrollment and available

for the analysis) with a 2:1 randomization will allow detection of an absolute difference of 28% with 80% power (i.e. 30% of women in the no IVR arm and 58% of women in the study IVR arm).

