In addition to looking at shifts in the Nugent score, within arm descriptions, and between arm comparisons, will be done to assess clinically meaningful changes in quantitative measures of vaginal flora (defined by more than ≥ 1 log change in dominant members of the microflora) and to assess differences in the quantitative levels of these microflora between arms during follow-up. Quantitative vaginal cultures and vaginal biomarkers will be assessed only at the US sites and therefore the available sample size for these analyses will be 102 women (68 in the study IVR arm and 34 in the no IVR arm). A sample size of 102 women with a 2:1 randomization will allow detection of a medium effect size of 0.59 with 80% power in comparing quantitative levels between arms.

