10.8.3 Secondary and Exploratory Analyses

Sexual behavior and vaginal hygiene practice

The behavior measures will be collected via ACASI at the Enrollment Visit, follow-up visits, and at the 16-Week/Study Termination Visit. The sexual behaviors and vaginal hygiene practices include the number of sexual partners in the past 3 months, the number of new partners (not asked at enrollment), frequency of sex in the past 7 days, condom use in the past 7 days, condom use during the last sex act, anal sex in the past month, condom use during anal sex in the past month, and vaginal hygiene practices (list of various items/products inserted) in the past 7 days.

For each of the longitudinal behavioral measures, the mean (or the percentage if binary) in each visit in each arm will be computed and tabulated. The generalized estimation equation (GEE) method will be used to assess the difference of each measure between the two arms, accounting for within-subject correlation.

Acceptability

To assess acceptability of the study IVR, the number and percentage of participants in the study IVR arm experiencing at least one negative report of acceptability, including genitourinary discomfort, ring insertion/removal issues, expulsions, and/or changes in participant and/or partner sexual feeling during follow-up will be presented. This binomial proportion will be used to assess the acceptability of the study IVR along with its corresponding 95% confidence interval.

The above acceptability analysis will be supplemented by presenting the above proportion by site along with its corresponding 95% confidence interval.

Vaginal Flora

In order to assess the effect of the study IVR on the vaginal flora of sexually active, HIV-uninfected women, clinically significant changes in vaginal flora will be evaluated by the Nugent score with shift tables from baseline (Enrollment) to follow-up visits at week 4, 8, 12, and 16 to assess the effect on vaginal flora.

The Nugent score is graded 1 to 10 as follows:

- | | |
|------------------|---------|
| 1. Normal, | 0 to 3 |
| 2. Intermediate, | 4 to 6 |
| 3. BV, | 7 to 10 |

Any shift from normal at baseline to intermediate or BV at a follow-up visit, or intermediate or BV at baseline to normal at a follow-up visit, will be considered a clinically meaningful change in vaginal flora. The proportion of changes within each arm will be reported and will be formally compared using the Fisher exact test (from the

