derivation of the two-sample case of the McNemar's test of change). Please refer to Levin and Serlin⁶⁸ for more details. In addition, this analysis will be supplemented by an analysis using the change from baseline in Nugent score for each woman. Comparison for differences in change from baseline between arms will be assessed by using an unpaired t-test or a Mann-Whitney test (if distribution of change scores does not allow the use of the unpaired t-test).

In addition to looking at shifts in the Nugent score and changes in biomarkers, within arm descriptions, and between arm comparisons will be done to assess clinically meaningful changes in quantitative measures of vaginal flora (defined by more than ≥ 1 log change in dominant members of the microflora) and to assess differences in the quantitative levels of these flora between arms during follow-up. Note that this analysis can only be performed using women from the US sites since quantitative cultures will not be conducted for women at the India site.

Biofilms

In the US sites, the percentage of women with biofilms on study IVR surface after 12 weeks of use will be computed for the IVR arm.

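### The 1-log rule for a clinically meaningful quantitative-culture change has no direction and does not define 'dominant', so the between-arm proportion can mix gain and loss of lactobacilli

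*Protocol*

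**What the plan says.** The Protocol Summary and Section 10.2.2 name the endpoint, "Changes in vaginal flora from enrollment to week 12 as measured by Gram stain Nugent score and quantitative culture", and note that culture is available from the US sites only. That line names the measures and contains no rule.

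The rule is in Section 10.4.4 and is repeated in Section 10.8.3. Clinically meaningful changes in quantitative flora are "defined by more than ≥ 1 log change in dominant members of the microflora", to be described within arms and compared between arms. Neither section gives a sign, names an organism, or says whether dominance is judged at enrollment, at follow-up or from a fixed list. The same sentence in Section 10.8.3 adds a comparison of "quantitative levels of these flora between arms during follow-up", and Section 10.4.4 has a near-identical clause.

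For Nugent score the protocol deals with direction in two ways. Section 10.4.4 keeps the directions apart: the proportion changing "from normal to abnormal will be compared as well as the one from abnormal to normal". Section 10.8.3 puts both under one label: a shift from normal to intermediate or BV, "or intermediate or BV at baseline to normal at a follow-up visit, will be considered a clinically meaningful change in vaginal flora".

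On the biology, Section 2.7.2 says that H2O2-"producing lactobacilli in the vagina offer a protective effect against sexually transmitted infections". It also makes documentation of flora change part of confirming the ring's safety. Section 2.2 reports that an earlier study of another ring found such lactobacilli increased, and says their presence (H2O2-producing) "lactobacilli is beneficial to vaginal health and it has been suggested that further studies be conducted to confirm these findings". Of a further ring study it says "No increases in pathogenic bacteria were found upon examination of vaginal cultures".

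**The concern.** By the protocol's own account, losing and gaining protective lactobacilli are opposite results for safety, and a gain is a realistic outcome because one has been seen with another ring. A threshold without a sign gives both the same label. If the proportion of women with such a change is compared between arms, a rise in losses can be offset by a fall in gains. A ring that only increased lactobacilli could also appear as an excess of clinically meaningful change.

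The restriction to dominant members raises a second, smaller question. In a woman whose flora is dominated by lactobacilli, a several-log rise in another organism that stays below them may not count. Whether it counts depends on a word that the protocol leaves undefined. Also, 'more than' followed by '≥ 1' does not settle the case of exactly 1 log.

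**Working it through.** **1. The protocol's own culture figure.** Section 10.4.4 states a detectable effect of 0.59 SD with 80% power for comparing quantitative levels, with 68 and 34 women. Alpha and sidedness are not stated for this figure; two-sided 5% is assumed.

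- SE of the standardised difference = √(1/34 + 1/68) = 0.210
- 0.59 / 0.210 = 2.809
- Power = Φ(2.809 − 1.960) = Φ(0.849) = 0.802

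A t-test calculation gives 0.794. The figure reproduces. It applies to continuous levels; the protocol gives no power figure for the 1-log proportion.

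**2. What the undirected rule can do to the proportion.** Inputs from the protocol: 68 ring and 34 no-ring women at the US sites. Assumed inputs: all rates of 1-log gain and loss of lactobacilli, because the protocol gives none; a two-sided Fisher exact test at 5%; and gain and loss mutually exclusive from enrollment to Week 12.

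For one woman, P(undirected change) = P(loss) + P(gain). Power is the sum, over all outcome pairs (x, y) with Fisher p ≤ 0.05, of Bin(x; 68, p_ring) × Bin(y; 34, p_none). The no-ring arm is held at 15% loss and 15% gain, so its undirected rate is 15% + 15% = 30%.

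| Ring arm: loss / gain | Undirected, ring vs none | Power, undirected | Loss only, ring vs none | Power, loss only |
|---|---|---|---|---|
| 35% / 5% | 40% vs 30% | 14% | 35% vs 15% | 54% |
| 40% / 5% | 45% vs 30% | 27% | 40% vs 15% | 73% |
| 30% / 0% | 30% vs 30% | 4% | 30% vs 15% | 34% |
| 35% / 15% | 50% vs 30% | 45% | 35% vs 15% | 54% |
| 40% / 15% | 55% vs 30% | 63% | 40% vs 15% | 73% |

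In the first three rows gains fall while losses rise, and the two partly or wholly cancel. In the last two rows gains are equal in both arms, and the cost of ignoring direction is about 10 percentage points of power. A normal approximation for the last row gives 67% against 75%, the same picture.

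**3. The mirror case.** Suppose the ring only increases lactobacilli: gain 35% against 15%, loss 15% in both arms. The undirected rates are 35% + 15% = 50% and 15% + 15% = 30%, and the chance of a significant difference is 45%. This is not a false-positive rate, since flora did change. It shows that the label would not tell benefit from harm.

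**4. Dominance.** If dominance is fixed at enrollment, a rise in an initially non-dominant organism is not counted. If it is judged at follow-up, an organism that overgrows can qualify, while one that rises but stays below the lactobacilli does not. The text supports either reading, so two analysts could score the same culture differently.

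**The case against.** The strongest reply is that the sentence containing the rule also plans a comparison of quantitative levels between arms. Levels keep their sign, and this is the only culture analysis the protocol powers. Section 10.8.3 also compares change from baseline in Nugent score between arms with its sign, and Nugent scores come from all three sites. A reader might infer from the unsigned rule that the culture data cannot show whether the ring harms flora. The documents do not support that inference, for the reasons just given.

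Second, pooling of gains and losses is inferred from the absence of a sign; it is not written into the culture rule. A table of increases and decreases by organism would satisfy the text. This is fair. The parallel Nugent definition in Section 10.8.3, however, expressly gives both directions one label, so pooling is the natural reading of the culture rule as well.

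Third, a reader might conclude that overgrowth of a non-dominant pathogen is definitely not scored. That depends on how 'dominant' is read, and so does the scope of the levels comparison: 'these flora' could mean the dominant members or the vaginal flora generally. Only 'may not be scored' can be defended.

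Fourth, the powers rest wholly on assumed rates, and the large gaps need gains to fall as losses rise. That also stands. The endpoint is secondary, its culture part is US-only, and Section 3.2 describes the objective as descriptive.

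**Conclusion.** The point holds in limited form. The protocol fixes a definition of clinically meaningful culture change that has no direction and uses an undefined term. This fits poorly with its own statement that lactobacilli are protective and with the safety purpose it gives the flora data. The affected result is the between-arm proportion with a 1-log change. The signed comparison of levels remains, so direction is not lost from the plan.

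The size depends on rates that the protocol does not give. With 68 and 34 women and a two-sided Fisher test at 5%, power to see a harmful shift falls from 54% to 14% when losses go from 15% to 35% and gains from 15% to 5%. It falls only from 54% to 45% when gains stay at 15% in both arms. Since the cultures are already planned, the rule is worth correcting as a low-cost improvement to a secondary analysis.

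**What to change.** In Sections 10.4.4 and 10.8.3, replace the single rule with two proportions per organism group, compared between arms from enrollment to Week 12: women with a decrease of ≥1 log10, and women with an increase of ≥1 log10. The groups would be lactobacilli and the other groups cultured, whether or not dominant at enrollment, which removes the need to define 'dominant'. Write '≥1' in place of the present wording. Keep the comparison of quantitative levels.

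The cost is wording and a few more reported proportions in a descriptive, US-only secondary analysis. No new samples or visits are needed.

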1.1 Protocol Identification

Protocol Title: Expanded Safety and Adherence Study of a Non-medicated Intravaginal Ring

MTN Protocol Number: MTN-005

Date: October 19, 2010

2 INTRODUCTION

2.1 New Proposed Modalities in HIV Prevention

While the male condom is effective in preventing sexual transmission of HIV, its use is hampered by deeply rooted cultural and social barriers. About half of all HIV infections worldwide are among women, yet the only available female-controlled method of HIV prevention is the female condom. The fact that half of all HIV infections worldwide are among women indicates the pressing need for alternative prevention methods to stem the spread of heterosexual HIV infection. Research continues on many different strategies targeted at the prevention of HIV transmission, including topical microbicides, oral pre-exposure prophylaxis, prevention case management, vaccines, treatment of sexually transmitted infection, and others.^{1, 2} Some studies have provided strong evidence that male circumcision can reduce female to male transmission of HIV² but there remains a critical need for female controlled methods of prevention. Use of an intravaginal ring (IVR) to deliver microbicide products is a novel investigational method for prevention of heterosexual transmission of HIV, and one that may circumvent potential difficulties related to adherence to daily or coitally dependent regimens of microbicide use. Evaluating the safety of this delivery method as well as adherence, are necessary first steps prior to evaluating the efficacy of vaginal rings for the prevention of HIV.

2.2 Intravaginal Rings

There are currently three IVRs (NuvaRing[®], Estring[®] and Femring[®]) that have received US Food and Drug Administration (US FDA) approval.³⁻⁵ NuvaRing[®] (Organon) is approved for use as a vaginal contraceptive, it releases etonogestrel and ethinyl estradiol, and must be replaced every month. It was also approved for use in India in November 2009.⁶ Estring[®] (Pfizer) is a hormone replacement system that releases a low dose of estradiol and must be replaced every three months. Like Estring[®], Femring[®] (Warner Chilcott) must be replaced every three months and is another hormone replacement therapy that releases estradiol (available in two different dosing options)

Safety studies have been conducted for all three rings currently approved by the US FDA. Published safety data from these studies include results from physical, pelvic, and colposcopic exams. In general, the adverse events (AE) reported in these studies were mild and only a small percentage were found to be related to the device. No clinically relevant changes or abnormalities were found upon examination in study participants.⁷⁻¹⁰ Nonetheless, as with any vaginal device, there is consensus that such products are not appropriate for women who are prone to vaginal irritation or ulceration.^{3,4}

The Population Council has been instrumental in developing vaginal rings for contraceptive effectiveness. They have developed and carried out numerous safety and effectiveness studies on Progering[®], a platinum-catalyzed, silicone elastomer

progesterone vaginal ring (PVR) for lactating women.¹¹⁻¹⁵ While not an effective contraceptive method for cycling women, Progering[®] can be used by nursing women to extend the contraceptive effectiveness of lactation. The method was well accepted and has effectively protected women from pregnancy in several research studies.^{12, 14-16} A Chilean company is currently manufacturing Progering[®] which is licensed for distribution in Bolivia, Chile, Ecuador, and Peru.¹⁷ The Population Council recently completed Phase 3 studies for a 1-year contraceptive ring made of platinum-catalyzed silicone elastomer that releases Nestorone (NES), a synthetic progestin and a low dose of ethinyl estradiol (EE).¹⁷ While the two rings are composed of the same material, the Progering[®] has a matrix delivery system while the NES/EE ring has a two-core delivery system. The Population Council has a well-established record of product development in the reproductive health field and an interest in pursuing the IVR as a platform for candidate microbicide delivery. Based on the Population Council's experience with this ring and the available data on the commercially available product, the non-medicated version of Progering[®] will be used in MTN-005.

Limited studies have also been conducted to determine the effect of IVR use on vaginal microflora and pathogenic organisms. A study evaluating changes in the quantities of vaginal cells, aerobic and anaerobic bacteria, *Chlamydia trachomatis*, *Gardnerella vaginalis*, yeast, and *Trichomonas vaginalis* was conducted in 59 women using a combined contraceptive vaginal ring made of Silastic[®] with an ethylene vinyl acetate (EVA) core for either a 21, 28, 42, or 56 day cycle.¹⁸ No increases in pathogenic bacteria were found upon examination of vaginal cultures. Another study conducted with a Silastic[®] ring with a polyethylene vinyl acetate core and containing a combined hormonal contraceptive, evaluated the effect of the ring on bacterial flora over 20 cycles of use among 76 women.¹⁹ The investigators found no significant changes in bacterial flora over the course of the study. Two studies conducted among 92 women with NuvaRing[®] showed no adverse effects on vaginal flora as measured by Nugent score.^{20, 21} Interestingly, a NuvaRing[®] study conducted by Veres et al.²⁰ found an increase in hydrogen peroxide (H₂O₂) producing *Lactobacillus* colonies as measured by quantitative culture. Presence of H₂O₂-producing lactobacilli is beneficial to vaginal health and it has been suggested that further studies be conducted to confirm these findings.

The success of IVRs in delivering effective contraceptive and hormone-replacement methods has spurred an interest in developing IVRs expressly for the prevention of HIV. Phase 1/2 safety studies have been conducted by the International Partnership for Microbicides (IPM) for an IVR containing dapivirine, a non-nucleoside reverse transcriptase inhibitor (NNRTI).²²⁻²⁵ The IVRs used in these studies (both active and placebo) have been well tolerated by most study participants.

